3.1 General Considerations

Except where otherwise specified, the following general principles apply to the planned statistical analyses. All statistical analysis will be conducted using SAS version 9.3 or later (SAS Institute Inc., Cary, NC) or other widely-accepted statistical or graphical software as required.

3.1.1 Descriptive Statistics

Continuous data will be summarized with mean, standard deviation, median, minimum, maximum, and number of evaluable observations. Categorical variables will be summarized with frequency counts and percentages. Confidence intervals may be presented, where appropriate, using the t-distribution for continuous data and Clopper-Pearson Exact method for categorical variables. Time to event analyses will be reported using Kaplan-Meier graphs.

3.1.2 Study Day

Study Day 0 is the date of the index procedure. Day in study will be calculated relative to the index procedure as follows:

Study Day = Assessment Date – Index Procedure Date

For each subject, duration in study will be based on last study contact date which is the latest date of all follow-up visits, assessments, adverse event onset or resolution, and study exit including date of death.

Duration variables will be calculated as follows:

Stati	stical Analysis Plan	Pa	ge 8 of 9
Sponsor	Study		Version
Farapulse	FARA-FREE II PMCF Stu	dy	1.1

Duration Days = Start Date - End Date

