3.4.2.1 Primary Analysis

The endpoint will be evaluated using the ITT analysis set. The endpoint will be presented using Kaplan-Meier survival analysis. The number of subjects at risk and the survival estimate will be presented at 30 day intervals from the index procedure date through Day 365.

For subjects with an event, the date of the first event occurrence will be used as the basis for event time. For subjects without an event, the date of censoring will based on date was last evaluable for the endpoint. If a subject's censoring time without event is at or after the window open date of the month 12 visit window, the censoring time will be set to Day 366.

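### SAP 3.1.2 writes the duration formula in reverse order, so duration in study comes out negative if the rule is followed literally

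*SAP*

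**What the plan says.** SAP section 3.1.2 sets out two date derivations.

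- **Study Day.** The origin is fixed first: "Study Day 0 is the date of the index procedure". The formula follows: "Study Day = Assessment Date – Index Procedure Date". This is later minus earlier for anything after the procedure.
- **Duration.** The section says that "duration in study will be based on last study contact date which is the latest date of all follow-up visits", and goes on to list other kinds of contact date, ending with study exit or death. It then gives a general rule, "Duration variables will be calculated as follows", and the formula "Duration Days = Start Date - End Date".

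Nothing else in the SAP takes an absolute value, redefines the start and end dates, or gives another rule for durations in days. Section 3.1 makes its general principles binding unless something else is specified, and no later section overrides this formula.

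**The concern.** An end date cannot fall before its own start date, so a start-minus-end rule can return only zero or a negative number. The Study Day formula a few lines earlier subtracts in the other direction, so the section is inconsistent with itself.

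This is a derivation rule that programmers are meant to implement. Programming and independent validation are normally checked against the SAP. As the line stands, a program that follows it produces impossible follow-up times, and a program that gets the right answer departs from the SAP. Section 3.1.1 calls for continuous data to be summarized by mean, standard deviation, median, minimum and maximum, so a wrong sign would carry into most of those figures for any variable derived this way.

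**Working it through.** The SAP gives no worked duration to reproduce, so the check applies each formula to the same intervals.

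**Inputs**
- Duration rule as written: start minus end (SAP 3.1.2).
- Study Day rule: assessment date minus index date, with the index date as Day 0 (SAP 3.1.2).
- Illustrative intervals from the index procedure: 0, 1, 7, 90 and 365 days. These are chosen for the check and are not trial data.
- Assumption: duration in study starts at the index procedure. The SAP names its end date but not its start date. With an earlier start, such as consent, the sign would still be negative.

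**Step 1: single intervals**

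| Interval (days) | Study Day | Duration as written | Duration with terms swapped |
|---|---|---|---|
| 0 | 0 | 0 | 0 |
| 1 | 1 | -1 | 1 |
| 7 | 7 | -7 | 7 |
| 90 | 90 | -90 | 90 |
| 365 | 365 | -365 | 365 |

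For the last row, as written: 0 - 365 = -365. Swapped: 365 - 0 = 365, which equals Study Day. A same-day interval gives 0 either way.

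**Step 2: summary statistics, treating the five intervals as a small sample**
- Mean: (0 + 1 + 7 + 90 + 365) / 5 = 463 / 5 = 92.6. As written, -92.6.
- Median: 7. As written, -7.
- Minimum and maximum: 0 and 365. As written, -365 and 0, so the longest follow-up is reported as the minimum.
- Standard deviation: the squared deviations from the mean sum to 98,501.2; 98,501.2 / 4 = 24,625.3, and its square root is 156.9. Changing every sign leaves this the same.

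**Step 3: what uses the formula**
- *Primary safety (SAP 3.4.1.1)*: subjects with at least one qualifying event over all ITT subjects. No duration enters.
- *Primary effectiveness (SAP 3.4.2.1)*: "the date of the first event occurrence will be used as the basis for event time", with results shown at 30-day intervals from the index procedure through Day 365 and late censoring set to Day 366. This is the positive Study Day scale, and the section does not cite the duration formula.
- *Procedural outcomes (SAP 3.5.1)*: procedure, dwell, ablation and fluoroscopy times each carry their own definition and are measured within a procedure. A formula in whole days does not usefully apply to them.
- *Duration in study (SAP 3.1.2)*: named immediately before the formula, and the only duration in days that the SAP names.

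**The case against.** The best case for leaving this alone is that it is an evident slip. The Study Day formula beside it shows the intended order, a negative follow-up time is impossible on its face, and any first output would expose it. Only the sign is wrong, so no information is lost. If duration in study starts at the index procedure, it equals the Study Day of last contact, which the neighbouring formula already gives with the right sign.

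All of that stands, and it limits the severity. It does not make the line correct. A silent repair in code would leave an undocumented departure from the SAP.

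The objection also rules out some wider readings that a reader might infer:
- *Every duration turns negative.* Same-day intervals give 0, and the procedural times have their own definitions.
- *Adverse-event durations will be misreported.* The SAP plans no such summary. Section 3.1.2 mentions event onset and resolution only as candidate dates for last contact.
- *The primary results are at risk.* Neither primary analysis is shown to use the formula.

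**Conclusion.** The formula is wrong as written, and the effect is small. Any duration of one day or more derived from it has the right size and the wrong sign; on the SAP's text, that means duration in study. Its mean and median would change sign, its minimum and maximum would change sign and swap, and its standard deviation would not move.

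The conclusion rests on reading the line as ordinary subtraction and on the end date falling on or after the start date. The figure of -365 for a subject last contacted on Day 365 also assumes a start at the index procedure. No trial conclusion is shown to depend on the error, so this is a low-severity correction.

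**What to change.** In SAP 3.1.2, change the line to: Duration Days = End Date - Start Date. This matches the Day 0 convention and the order of subtraction used for Study Day. No extra day should be added as part of this correction: an inclusive count would turn 365 into 366, and the SAP does not ask for one.

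The cost is one line in the next SAP revision. No endpoint, analysis set, sample size or clinical procedure changes. If durations have already been programmed, confirm that the code takes end minus start.

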3.1.3 Visit Windows

Unless otherwise specified, visit based assessments will be analyzed for each analysis time point according to the nominal visit entered in the Case Report Form (CRF) regardless of if it is out of window.

3.1.4 Statistical Significance

No formal hypothesis tests will be conducted. Any p-values reported will be descriptive and will be performed at the two-sided 0.05 significance level. P-values will be rounded to three decimal places. If a p-value is less than 0.001 it will be reported as "<0.001". If a p-value is greater than 0.999, it will be reported as ">0.999".

3.1.5 Precision

Unless otherwise specified, the following conventions will apply for data display. In general, percentages will be displayed to 1 decimal place. Percentages <0.05% will be reported to 2 decimal places. For continuous parameters, means and medians will be reported to 1 additional decimal place than the measured value while standard deviation will be reported to 2 additional decimal places than the measured value. Minimum and maximum values will be reported to the same precision as the measured value.

3.2 Analysis Populations

The following analysis populations are defined for analysis:

 ITT: The ITT analysis set is defined as all enrolled subjects except those who terminate their participation prior to the beginning of the Index Procedure

The primary safety and effectiveness analyses will be summarized in the ITT analysis set.

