PRIMARY SAFETY ENDPOINT:	The primary safety endpoint is the Composite Safety Endpoint (CSE) defined as the proportion of Safety Subjects with one or more of the following device- or procedure-related SAEs as adjudicated by the CEC based on protocol definitions. Early onset (within 7 days of an index or Rescheduled Index procedure: • Death • Myocardial infarction • Persistent phrenic nerve palsy • Stroke • Transient ischemic attack (TIA) • Peripheral or organ thromboembolism • Cardiac tamponade / perforation • Pericarditis • Pulmonary edema • Vascular access complications • Heart block • Gastric motility/pyloric spasm disorders Late onset (any time through the completion of 12 month follow-up visit) • Pulmonary vein stenosis • Atrio-esophageal fistula					
Additional Safety Analyses:	 Severe Ablation Complications Nonserious / Serious CSEs Post-Blanking Direct Current Cardioversions Post-Blanking Arrhythmia Hospitalizations Any Related SAE Any Related Stroke or TIA 					

PRIMARY EFFECTIVENESS ENDPOINT:	 The primary performance endpoint is Treatment Success in Modified Intent-to-Treat (mITT) subjects, defined as: Acute Procedural Success, AND 1. Chronic Success, defined as freedom from: a. At the Index / Rescheduled Index Procedure: Use of a non-PFA treatment modality for PVI b. After the Blanking Period: i. Occurrence of any Detectable AF, AFL or AT (excluding CTI-dependent AFL confirmed by EP study) ii. Cardioversion for AF, AFL or AT (excluding for CTI-dependent AFL) iii. Use of any Type I or Type III antiarrhythmic medication for the treatment of AF, AFL or AT c. At any time: i. Re-ablation for AF, AFL or AT (other than for CTI-dependent AFL)
Additional Effectiveness Analyses:	 Acute Procedural Success Acute Vein Success Chronic Success Chronic Success Allowing Re-ablation Chronic Success Allowing AADs Treatment Success Allowing Re-ablation Treatment Success Allowing AADs Treatment Success with PVI/CTI Only Early Recurrence of AF Rate of Re-ablation AF Symptom Assessment

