3.4.1.1 Primary Analysis

The endpoint will be evaluated using the ITT analysis set. The endpoint will be presented as the frequency and percent of subjects experiencing one or more CSE as well as the total number of events.

The numerator will include subjects with one or more CSE and the denominator will include all ITT subjects. The individual components of the CSE will also be summarized.

The proportion will be compared against the performance goal (PG) of 17%. The endpoint will be met if the upper bound of the 95% exact binomial CI around the proportion is less than the PG.

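### The SAP uses one ITT set for both primary analyses, while the protocol names Safety Subjects for safety and mITT for performance, so the primary denominators are unreconciled.

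*SAP*

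**What the plan says.** The protocol synopsis attaches a named population to each primary endpoint. The safety composite (CSE) is "defined as the proportion of Safety Subjects with one or more of the following device- or procedure-related SAEs". For effectiveness, "The primary performance endpoint is Treatment Success in Modified Intent-to-Treat (mITT) subjects". The synopsis defines neither set; it refers to the CIP (CS1169 Rev D), which is not among the documents reviewed here.

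The SAP defines one population, in section 3.2: "The ITT analysis set is defined as all enrolled subjects except those who terminate their participation prior to the beginning of the Index Procedure". It then says: "The primary safety and effectiveness analyses will be summarized in the ITT analysis set". Section 3.4.1.1 repeats this for safety: "The numerator will include subjects with one or more CSE and the denominator will include all ITT subjects". The decision rule in the same section is: "The endpoint will be met if the upper bound of the 95% exact binomial CI around the proportion is less than the PG". Section 3.4.2.1 uses the ITT set for the Kaplan-Meier analysis of effectiveness. Neither Safety Subjects nor mITT appears anywhere in the SAP.

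**The concern.** Both primary endpoints are judged against a fixed goal (17% for safety, 50% for performance), so the denominator is part of the decision rule. The two documents name different denominators and nothing links them.

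The sets need not coincide. The SAP's ITT set requires only that the procedure began, not that the study device was used. According to a footnote to the protocol's schedule of events, imaging for thrombus is done at the start of the procedure, before ablation. A subject stopped at that point who never comes back would stay in the SAP's ITT set without having been ablated. If Safety Subjects or mITT requires treatment, that subject is outside the protocol's set.

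Extra subjects at low risk of a CSE would lower the observed rate and make the 17% goal easier to meet. In the performance analysis the same subjects could lower the success estimate or leave it almost unchanged, depending on how they are coded. If the choice of set is still open when results are known, it can be made with the results in view.

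**Working it through.** **Inputs.** Protocol synopsis, sample size section: expected CSE rate 9%, goal 17%, one-sided type I error 2.5%, 80% power, minimum 150; expected success 65%, goal 50%; up to 15% losses; about 180 subjects. SAP 3.4.1.1: safety is met if the upper 95% exact bound is below 17%. Let m be the number of ITT subjects outside the protocol's set. The documents do not give m; I assume 2, 5 or 9 of 180.

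**1. The plan's own figure.** With n = 150, the exact test passes at 16 or fewer events: P(X ≤ 16 | 150, 0.17) = 0.0207 and P(X ≤ 16 | 150, 0.09) = 0.807. The stated 150 is reproduced. For losses, 150 / (1 − 0.15) = 176.5, or 177, consistent with about 180.

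**2. Can the verdict change?** The upper 95% exact bound for x events in n subjects is the 0.975 quantile of Beta(x + 1, n − x).

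| Events / subjects | Upper bound | Goal of 17% |
|---|---|---|
| 20 / 180 | 16.6% | met |
| 20 / 175 | 17.1% | not met |
| 20 / 171 | 17.5% | not met |

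The largest passing count is 20 for n = 177 to 180 and falls to 19 at n = 176. Removing four subjects is therefore enough to move the cut-off by one event.

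**3. Chance of passing safety when the true rate in the protocol's set is 17%.** The ITT rule (20 or fewer events in 180) is applied to 180 − m subjects at 17% plus m subjects at risk r. For r = 0 this is P(Bin(180 − m, 0.17) ≤ 20). For r = 8.5% (half of 17%, an assumption) it is the sum over j of P(Bin(m, 0.085) = j) × P(Bin(180 − m, 0.17) ≤ 20 − j).

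| m | r = 0 | r = 8.5% | Protocol's set as denominator |
|---|---|---|---|
| 0 | 1.9% | 1.9% | 1.9% |
| 2 | 2.2% | 2.0% | 2.2% |
| 5 | 2.7% | 2.3% | 1.6% |
| 9 | 3.6% | 2.6% | 2.1% |

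The last column uses the exact cut-off for 180 − m subjects (20, 20, 19 and 19 events) and counts only their events. It stays below 2.5% throughout.

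**4. Performance.** If the m subjects count as failures, a true 65% reads as 0.65 × (180 − m) / 180:
- m = 2: 0.65 × 178 / 180 = 64.3%
- m = 5: 0.65 × 175 / 180 = 63.2%
- m = 9: 0.65 × 171 / 180 = 61.8%

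If they are instead censored close to Day 0, they leave the risk set before any post-blanking event can occur, and the Kaplan-Meier estimate at Day 365 hardly moves. SAP 3.4.2.1 does not say which applies to a subject in whom no ablation was attempted.

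**The case against.** The strongest reply is that different labels do not prove different subjects. The SAP's ITT set already drops those who leave before the procedure begins, so it is a modified ITT in all but name. If the CIP defines Safety Subjects as everyone whose procedure began, the two safety denominators are identical. This stands: the synopsis defines neither set, so no difference in membership can be shown.

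A reader might infer that subjects never exposed to the device cannot have a CSE and must dilute the rate. The documents do not support that. The composite counts procedure-related as well as device-related events, and vascular access complications, for example, can occur without ablation. Zero risk is therefore the extreme case, and at half the 17% risk most of the inflation goes.

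The thrombus route is also narrow. The protocol's planned procedures say that subjects who screen positive are rescheduled, so only those never treated afterwards remain. No passage suggests that this would reach 9 of 180.

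Nor do the documents support the inference that untreated subjects must count as acute failures. The SAP is silent on their coding, and if they are failures the effect on performance is conservative.

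SAP 3.1.4 says that no formal tests will be done. That does not settle the matter, because SAP 2.1.1, 2.1.3 and 3.4.1.1 keep pass/fail rules against the goals. It may also be said that the SAP (version 1.1 of December 2020, titled FARA-FREE II) simply predates the May 2022 FARA-FREEDOM synopsis. That may explain the mismatch, but it leaves it in place.

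**Conclusion.** The conflict over which population is primary is explicit and should be resolved. A biased safety rate is not demonstrated: that would need definitions and a count that the documents do not give.

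The possible effect on safety runs from none, if Safety Subjects equals everyone whose procedure began, to a pass probability of 3.6% instead of the planned 2.5%, if 9 of 180 ITT subjects fall outside the set and carry no risk. With 2 such subjects it stays under 2.5% on either risk assumption. A single result near the boundary could change verdict, as 20 events in 180 against 20 in 175 shows. For performance, the direction depends on coding. In the conservative case the reduction from 65% is at most about 3 points over the assumed range, to 61.8%, still well above the 50% goal.

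**What to change.** In SAP 3.2, carry over the CIP's definitions of Safety Subjects and mITT. Make Safety Subjects the denominator in 3.4.1.1 and mITT the set for 3.4.2.1, and keep the present ITT set as a sensitivity analysis for both. If the CIP's definitions turn out to match the present ITT set, say so in the SAP. State in 3.4.2.1 how a subject with no attempted ablation is coded, and report how many subjects fall in ITT but outside each primary set. All of this should be fixed before the outcome data are analysed.

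The cost is minor SAP wording and population flags, with no new data. The CSE percentage may come out slightly less favourable.

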3.3 Demographics and Baseline Characteristics

Descriptive statistics will be presented for all clinically-relevant baseline demographic, medical history, and clinical characteristic variables.

3.4 Analysis of Study Endpoints

3.4.1 Primary Safety Endpoint

The primary safety outcome is the Composite Safety Endpoint (CSE) defined as the incidence of the following early-onset and late-onset serious adverse events (SAEs) which are device- or procedure-related, as adjudicated by the CEDMC.

Stati	stical Analysis Plan	Pa	ge 9 of 9
Sponsor	Study		Version
Farapulse	FARA-FREE II PMCF Stu	dy	1.1

3.4.1.1 Primary Analysis

The endpoint will be evaluated using the ITT analysis set. The endpoint will be presented as the frequency and percent of subjects experiencing one or more CSE as well as the total number of events.

The numerator will include subjects with one or more CSE and the denominator will include all ITT subjects. The individual components of the CSE will also be summarized.

The proportion will be compared against the performance goal (PG) of 17%. The endpoint will be met if the upper bound of the 95% exact binomial CI around the proportion is less than the PG.

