PROCEDURAL Assessments:	 Assessments of duration for procedure components a. Procedure time (initiation of venous access to venous access closure). b. Left atrial dwell time (total time an ablation catheter is in the left atrium [LA]) c. Total ablation time (first ablation to last ablation) d. Fluoroscopy time (total duration of exposure). Characterization of lesion sets: a. PVI ablations b. CTI ablations c. For subjects undergoing required LA ablations for an accessory pathway, AVNRT, left-sided AFL or incessant AT, a description of lesion sets utilized
QUALITY OF LIFE MEASURES	Subjects will undergo assessment with the EQ-5D-3 L instrument and Atrial Fibrillation Effect on Quality of Life (AFEQT) questionnaire at baseline and 12 months.

	1				
SAMPLE SIZE Considerations	Sample size requirements for safety: Sample size is estimated assuming an underlying CSE rate of 9% compared to a performance goal (PG) of 17% using a binomial exact test. Assuming 80% power and one-sided Type I error of 2.5%, a minimum sample size of 150 is required.				
	Sample size requirements for performance: Sample size is estimated assuming an expected percent success of 65% compared to a PG of 50% using a binomial exact test. Assuming 80% power and one-sided Type I error of 2.5%, a minimum sample size of 85 is required.				
	Number of subjects: The sample requires 150 analyzable subjects to meet both safety and performance calculations. To allow for up to 15% subject losses, the study size has been set at approximately 180 subjects.				
Clinical Events Committee	An independent panel of 3 electrophysiologists will review AEs, adjudicate seriousness and relatedness of potential SAEs and adjudicate primary safety and performance outcomes.				
ARRHYTHMIA CORE Laboratory	A qualified Arrhythmia Core Lab (ACL) will be established to receive, review and assess all protocol-stipulated ECGs, EMs and Holter monitors.				

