2.1.1 Primary Safety Endpoint

The primary safety endpoint for this study is the Composite Safety Endpoint (CSE) defined as the incidence of the following serious adverse events (SAEs) which are device- or procedure-related, as adjudicated by the CEDMC based on the definitions contained in the Composite Safety Endpoint Definitions as outlined in the CIP.

Early onset (within 7 days of an index or protocol-specified reablation procedure)

- Death
- Myocardial infarction
- Persistent diaphragmatic paralysis
- Stroke
- Transient ischemic attack
- Peripheral or organ thromboembolism
- Pericardial effusion, hemorrhage or tamponade
- Vascular access complications
- Hospitalization
- Heart block

Late onset (any time during follow-up)

- Pulmonary vein stenosis
- Atrio-esophageal fistula

The proportion will be compare to the performance goal (PG) of 17%. The safety hypotheses are as follows:

 $H_0: \Pi \ge PG$ $H_A: \Pi < PG$

Statistical Analysis Plan		Pa	ge 6 of 9
Sponsor	Study		Version
Farapulse	FARA-FREE II PMCF Stu	dy	1.1

where Π is the proportion of subjects with one or more CSE. The null hypothesis will be rejected in favor of the alternative if the upper bound of the 95% binomial exact confidence limit is less than the PG. Sample size is estimated assuming an underlying CSE rate of 9% compared to the PG of 17%. Assuming 80% power and one-sided Type I error of 2.5%, a minimum sample size of 150 is required.

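### The primary safety proportion counts subjects lost without a recorded event as event-free; the effect on the 17% goal is probably small, but the SAP has no evaluability rule or sensitivity check

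*SAP*

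**What the plan says.** SAP 3.4.1.1 defines the primary safety proportion: "The numerator will include subjects with one or more CSE and the denominator will include all ITT subjects". The decision rule follows: "The endpoint will be met if the upper bound of the 95% exact binomial CI around the proportion is less than the PG". The performance goal is 17%.

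SAP 3.2 defines the denominator: "The ITT analysis set is defined as all enrolled subjects except those who terminate their participation prior to the beginning of the Index Procedure". Membership depends only on the procedure having begun. How long a subject is observed afterwards plays no part.

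The endpoint has two observation windows. Most components must occur within 7 days of the procedure. Pulmonary vein stenosis and atrio-esophageal fistula count later: in the protocol synopsis (Primary Safety Endpoint), "any time through the completion of 12 month follow-up visit"; in SAP 2.1.1, throughout follow-up. SAP 2.1.1 also opens the 7-day window after a protocol-specified reablation, whereas the synopsis ties it to the index or rescheduled index procedure.

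On losses, the synopsis (Sample Size Considerations) says: "The sample requires 150 analyzable subjects to meet both safety and performance calculations. To allow for up to 15% subject losses", and sets the study size at about 180.

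The only censoring rule in the SAP is in 3.4.2.1, for effectiveness. The safety analysis has no counterpart and no sensitivity analysis.

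**The concern.** A subject who leaves before the relevant window closes, with no CSE on record, stays in the denominator and adds nothing to the numerator. In effect the missing outcome is imputed as no event. The error runs in one direction: extra unobserved event-free subjects can only reduce the proportion and its upper confidence limit, and so favour meeting the goal. In a single-arm trial judged against a fixed goal, no comparator arm offsets this.

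The late components raise a second, descriptive issue. A statement that few or no subjects had stenosis or fistula, taken over all ITT subjects, would include people not followed to the 12-month visit.

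**Working it through.** **Inputs.** Goal 17%, assumed CSE rate 9%, one-sided Type I error 2.5%, 80% power, minimum n = 150 (SAP 2.1.1). Planned enrolment about 180, loss allowance up to 15% (synopsis, Sample Size Considerations). The number of ITT subjects is not known in advance; 180 is assumed below.

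**Formula.** For x events in n subjects, the exact (Clopper-Pearson) two-sided 95% upper limit is U(x, n) = the 97.5% quantile of Beta(x + 1, n − x). The goal is met if U < 17%.

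**The plan's own figure.** At n = 150, U(16, 150) = 16.74% and U(17, 150) = 17.52%, so the goal is met with 16 events or fewer. P(X ≤ 16) is 0.0207 at a true rate of 17% and 0.807 at 9%. The stated 150 reproduces. For losses, 150 / (1 − 0.15) = 176.5, so 177, in line with about 180.

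**All-ITT rule at n = 180.** U(20, 180) = 16.64%, met; U(21, 180) = 17.28%, not met. The most events allowed is 20.

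**Excluding L event-free subjects with no contact from Day 7 onward.**

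| L | n | Upper limits | Counts at which the result changes |
|---|---|---|---|
| 3 | 177 | U(20) = 16.91% | none |
| 4 | 176 | U(19) = 16.34%; U(20) = 17.004% | 20 only |
| 11 | 169 | U(19) = 16.999%; U(20) = 17.68% | 20 only |
| 12 | 168 | U(18) = 16.40%; U(19) = 17.10% | 19 and 20 |
| 27 (15% of 180) | 153 | U(16) = 16.43%; U(17) = 17.19%; U(20) = 19.46% | 17 to 20 |

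Near the design rate (9% of 180 = 16.2, about 16 events), even the last row changes nothing: U(16, 153) = 16.43%, still met.

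**Type I error if the L subjects are wholly unobserved.** The chance of 20 or fewer events among the 180 − L observed subjects, at a true rate of 17%, is 1.9% for L = 0, 2.5% for L = 4, 3.6% for L = 9 and 11.6% for L = 27. The nominal level is 2.5%.

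**Tipping point with the denominator held at 180.** The goal is missed once recorded plus unrecorded events reach 21, so the number of unrecorded events needed is 21 − x. At x = 20 it is one (21/180, 17.28%). At x = 16 it is five: four more give 20/180, 16.64%, met; five more give 21/180, not met.

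**The case against.** The strongest defence is that crude incidence over all treated subjects is a recognised safety convention, and that few subjects are likely to be unobserved in the window that matters. The synopsis schedules adverse-event assessment at the procedure, before discharge, at Day 7, Day 30, Day 90, Month 6 and Month 12. Any contact from Day 7 onward completes the early window, which covers 10 of the 12 components in SAP 2.1.1. Nothing in the documents shows that four or more treated subjects would have no such contact. This stands, and it is why the effect is judged small.

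A reader might infer from the 15% allowance that 27 of 180 subjects would be counted as safe without observation, that any result from 17 to 20 events is in doubt, and that the Type I error is 11.6%. The documents do not support that. The allowance is for all losses and has no timing. Some losses may precede the procedure and never enter ITT, and most later ones would be observed through Day 7 and would stay in under a Day 7 rule. The synopsis does not define analyzable either, so it does not settle how lost subjects were meant to be handled.

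A reader might also infer that losses after Day 7 can hide only the two late components. That holds for the index procedure but not under SAP 2.1.1, where a reablation opens a new 7-day window.

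Two further points stand in part. Keeping every subject with an event while dropping event-free subjects with short follow-up pushes the rate upward, so that denominator should not be shown alone. And the full investigational plan is not among the documents; it may define Safety Subjects, a term the synopsis uses without definition, or set an evaluability rule. If so, the SAP should cite it, because 3.4.1.1 as written is explicit about using all ITT subjects.

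**Conclusion.** The point holds as a modest, inexpensive improvement. The safety rule treats loss without a recorded CSE as absence of a CSE, the bias runs only towards meeting the goal, and the SAP neither limits nor tests it.

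On the assumption of 180 ITT subjects, exclusion alters the conclusion only if at least 4 event-free subjects lack any contact from Day 7 onward, and with 4 to 11 of them only at exactly 20 events. The 27-loss calculation is an outer bound and not the effect of the proposed change. The conclusion is more sensitive to unrecorded events than to the choice of denominator: one would reverse a result of 20/180, and five a result of 16/180. The documents do not show that the all-ITT proportion is wrong as a summary; the gap is that it stands alone.

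**What to change.** 1. In SAP 3.4.1.1, define the evaluable denominator as subjects with any CSE plus event-free subjects with contact at Day 7 or later after the index procedure. If the reablation window in SAP 2.1.1 is kept, also require contact at least 7 days after any protocol-specified reablation.
2. Report the two late-onset components by time-to-event with censoring at last contact, as 3.4.2.1 already does for effectiveness. Report the composite the same way as a sensitivity analysis.
3. Keep the all-ITT proportion alongside, with the number of subjects lacking Day 7 and Month 12 follow-up.
4. Add a tipping-point count: how many incompletely followed subjects would need a CSE for the 17% goal to be missed.
5. Align the terms ITT, Safety Subjects and analyzable between the SAP and the protocol, and fix the rule before results are known.

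The cost is SAP wording and one extra table, with no new visits, data or subjects. The reported CSE rate may be slightly less favourable.
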